計畫書英文摘要 (Protocol Synopsis)	文件編碼	KMUH/IRB/SOP/02.01.O
		版次	2024.00

I. Protocol title: Effects of an Exercise Snack Intervention on Employee Health and Work Performance: A Study at Kaohsiung Medical University

II. Objectives:

- (1) To develop brief exercise videos targeting different areas of physical discomfort (e.g., neck and shoulders, lower back, lower limbs), specific fitness goals (e.g., localized muscle stretching, targeted muscle strengthening, cardiorespiratory endurance, balance training), high-intensity interval training (HIIT), or the acquisition of specific movement skills (e.g., core stability, pelvic floor muscle contraction, and multi-directional pelvic mobility).
- (2) To design personalized exercise "menus" based on individual needs identified through a preliminary assessment, with the goal of improving adherence to voluntary exercise routines among staff.
- (3) To apply the concept of "exercise snacking" by implementing a daily routine of 3 to 8 brief exercise sessions, and to evaluate changes in staff members' physiological health, work performance, and exercise behavior after a 12-week intervention.

III. Test drug

1. **Name:** Not applicable
2. **Dosage form:** Not applicable
3. **Dose(s):** Not applicable
4. **Dosing schedule:** Not applicable
5. **Mechanism of action:** Not applicable
6. **Pharmacological category:** Not applicable

IV. Study design

1. **Control:** placebo
 - active (please specify name and dosage)
 - others

■ Uncontrolled
2. **Blinding:** open-label single blind double blind others
3. **Randomized:** yes no
4. **Parallel** cross-over others
5. **Sample/Data**
 - Biospecimens(IF sourced from the biological database No Yes , Name :)
 - Excluding DNA extraction
 - Including DNA extraction

	計畫書英文摘要 (Protocol Synopsis)	文件編碼	KMUH/IRB/SOP/02.01.O
		版次	2024.00

Medical record data

Questionnaires

Record (including measurements, interviews, voice recordings, video recordings)

Big data

Others: _____

6. Duration of study: from IRB approval ~to 12, 31, 2028, total 43 months

Duration of Enrollment: from IRB approval ~to 12, 31, 2028, total 43 months

Duration of treatment: from IRB approval ~to 12, 31, 2028, total 43 months

Duration of follow-up: from IRB approval ~to 12, 31, 2028, total 43 months

7. Multi-national multi-center(Taiwan) single center(Taiwan)

8. Number of subjects:

9. Is there any of the followings included DSMB, Data Safety Monitoring Board:

yes no

V. Assessment criteria

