1. Efficacy: Physical fitness assessments, Performance on functional movement tasks

2. Safety: Not applicable

3. Pharmacokinetics: Not applicable

4. Quality of life: Perceived stress scale, Work performance, Burnout inventory

VI. Selection criteria

1. Main inclusion criteria:

- (1) Currently employed at Kaohsiung Medical University or Kaohsiung Medical University Hospital.
- (2) Willing to participate in a 12-week exercise intervention, complete related questionnaires, and undergo physical performance assessments.

2. Main exclusion criteria:

- (1) Pregnant individuals, due to safety concerns related to exercise intensity and physical assessments.
- (2) Individuals with a diagnosed neurological disorder (e.g., stroke, Parkinson's disease).
- (3) Individuals experiencing severe pain in the upper or lower limb joints that interferes with their ability to complete the assessments.
- (4) Individuals assigned to high-intensity exercise who have unstable cardiac conditions (e.g., angina, myocardial infarction, heart failure).

	計畫書英文摘要 (Protocol Synopsis)	文件編碼	KMUH/IRB/SOP/02.01.O
		版次	2024.00

VII. Study procedures(summary)

1. Written informed consent must be obtained before any study specific procedures are undertaken.
 - (1) Recruitment announcements will be distributed through internal communication channels at Kaohsiung Medical University and its affiliated hospital.
 - (2) An introductory session and practical workshop on the "exercise snacking" program will be held.
 - (3) Participants will complete the informed consent form and attend a brief interview to complete questionnaires, including basic information (e.g., exercise habits) and a "personal issues and exercise needs assessment" to assist in designing a personalized exercise menu.
2. The process of the experiment (brief describe)
 - (1) Pre-intervention assessment: Participants will undergo baseline testing within one week prior to the start of the exercise intervention.
 - (2) Intervention period: Participants will engage in a 12-week exercise intervention program.
 - (3) Post-intervention assessment: Within one week following the intervention, participants will complete follow-up assessments.
 - (4) Follow-up check: One month after the completion of the program, participants will be contacted to assess whether they have continued engaging in the exercises independently without supervision from the research team.

VIII. Concomitant treatment:

1. Permitted: Not applicable

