2. Prohibited: Not applicable

IX. Statistical analysis

1. Statistical Method for Efficacy / Safety measurements:

This study adopts a cross-sectional data collection approach, and all data analyses will be conducted using SPSS version 20. The normality of continuous variables will be assessed using the One-Sample Kolmogorov-Smirnov test. Based on the results of the normality test, appropriate statistical methods will be selected.

If the data are normally distributed, parametric tests such as the paired-sample t-test will be used to compare pre- and post-intervention differences. If the data are not normally distributed, non-parametric tests such as the Wilcoxon signed-rank test will be employed.

Additionally, correlations between variables will be analyzed using either Pearson's correlation

	計畫書英文摘要 (Protocol Synopsis)	文件編碼	KMUH/IRB/SOP/02.01.O
		版次	2024.00

coefficient (for normally distributed data) or Spearman's rank correlation coefficient (for non-normally distributed data).

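### The paired tests named in IX.1 use only people who attend the post-test, so loss related to baseline biases the estimated change in this uncontrolled study, in either direction

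*Protocol*

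**What the plan says.** Protocol IX.1 sets the pre-post comparison according to a normality check. If the check passes, "parametric tests such as the paired-sample t-test will be used to compare pre- and post-intervention differences". If it fails, "non-parametric tests such as the Wilcoxon signed-rank test will be employed". Both tests are introduced as examples.

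The control item in section IV is marked "Uncontrolled". Section VII.2(2) states "Participants will engage in a 12-week exercise intervention program", and VII.2(3) adds "Within one week following the intervention, participants will complete follow-up assessments". Objective (2) aims at "improving adherence to voluntary exercise routines among staff", so uneven adherence is expected. Objective (3) asks about changes among staff after the programme, without limiting the question to those who are measured at the end.

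The protocol gives no expected dropout and no rule for a participant who has a baseline value but no post-test.

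**The concern.** A paired t-test or signed-rank test works on within-person differences, and a person without a post-test has none. Unless something is done first, that person drops out of the analysis and the baseline value is not used.

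In a randomised comparison, similar losses in the other arm may offset part of the resulting error. Here there is no other arm: the mean within-person change is the effect estimate, and selective loss enters it in full. Twelve weeks of voluntary daily exercise makes some loss plausible. If those lost differ at baseline from those who stay, regression to the mean alone shifts the estimated change. If those lost are the ones who did not benefit, the estimate is inflated by a separate route.

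**Working it through.** The plan has no figure of its own to reproduce: the text at hand shows no sample size, SD, effect size, correlation or dropout rate. Every value below is therefore an assumption.

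**1. Which people the test uses.** With 100 enrolled and 30 post-tests missing, a paired t-test on the data as collected uses 70 pairs (69 degrees of freedom). If the missing values are filled in first, the same test uses 100 pairs (99 degrees of freedom). The loss of people therefore comes from the test together with the absence of a rule for missing values.

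**2. General size.** Let d be the share without a post-test. Then

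bias = d × (mean change in those with a post-test − mean change in those without).

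| d | groups differ by 0.25 SD | groups differ by 0.5 SD |
|---|---|---|
| 10% | 0.025 | 0.05 |
| 20% | 0.05 | 0.10 |
| 30% | 0.075 | 0.15 |
| 40% | 0.10 | 0.20 |

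It is zero if d = 0 or the groups do not differ. In simulation (100 enrolled, SD of change 1, no change on average in all enrolled), a two-sided 5% test rejects at about 0.05 when the groups do not differ. Across these values of d it rejects in 0.06 to 0.13 of runs for a 0.25 SD difference and 0.07 to 0.32 for 0.5 SD.

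**3. Loss that depends on baseline.** With equal pre and post SDs and correlation ρ,

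bias = (ρ − 1) × shift,

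where shift is the mean baseline of attenders minus that of all enrolled, in SD units. Take logistic retention on baseline with intercept logit(0.70). Numerical integration gives:

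- log-odds 0.5 per SD: actual loss 31.0%, shift 0.147;
- log-odds 1.0 per SD: actual loss 33.1%, shift 0.277.

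For retention rising with baseline:

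- ρ = 0.7: −0.3 × 0.147 = −0.044 and −0.3 × 0.277 = −0.083 SD;
- ρ = 0.5: −0.5 × 0.147 = −0.074 and −0.5 × 0.277 = −0.139 SD.

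Against a true change of 0.30 SD, the range at ρ = 0.7 is 15% to 28% of the effect (0.044/0.30 and 0.083/0.30). If retention falls with baseline, the sizes are the same and the signs reverse.

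With intercept logit(0.90), the shifts are 0.053 and 0.119. The bias is then 0.016 to 0.036 SD at ρ = 0.7 and 0.027 to 0.060 SD at ρ = 0.5.

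**4. The alternative.** Simulation with 60 enrolled and 4000 runs per setting, using the settings of step 3 with intercept logit(0.70), reproduces the paired bias. The likelihood estimate that uses all baselines is off by at most about 0.005 SD. Its standard error is nearly the same: about 0.12 to 0.13 SD, against about 0.12 SD for the paired estimate, at ρ = 0.7.

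**5. Loss of non-responders.** Suppose 30% leave with no change and the rest improve by 0.30 SD. The change in all enrolled is 0.70 × 0.30 = 0.21 SD, and 0.30/0.21 = 1.43, so the paired estimate is 43% too high. If this loss is unrelated to baseline, the likelihood estimate is also 0.30 SD. The mixed model removes none of this bias.

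**The case against.** The strongest reply is that this is only silence on missing data, which a protocol commonly leaves to the SAP, and the SAP is not at hand. That stands in part. Silence alone is not the fault, and the tests are named as examples. What remains is that the methods IX.1 does name are the ones exposed to selective loss, and a method that uses every baseline is available at almost no cost in precision.

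A reader might infer that the protocol restricts its analysis to people who complete the programme. It does not say so. VII.2(3) schedules the post-test for participants without any condition on adherence, so someone who stopped exercising but attends stays in the paired analysis. Inclusion criterion (2) also asks for people who are "Willing to participate in a 12-week exercise intervention, complete related questionnaires, and undergo physical performance assessments", which may limit loss. That those who stop exercising are the likeliest to miss the post-test is plausible, but the protocol offers nothing to show it.

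A reader might also infer that the paired estimate must be too favourable. Step 3 shows that it can equally be too small. Nor does a mixed model cure every kind of loss, as step 5 shows.

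Finally, every magnitude is assumed. That also stands, and it limits the claim to what could happen under stated conditions.

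**Conclusion.** The point holds in a limited form. Applied as written to the data collected, the tests in IX.1 describe change in post-test attenders, and in an uncontrolled study baseline-related loss biases that change in either direction.

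Under the assumptions of step 3, at about 31% to 33% loss, the bias is 0.04 to 0.08 SD at correlation 0.7 and 0.07 to 0.14 SD at 0.5. It is smaller at lower loss and zero if nobody is lost or loss is unrelated to change. The 43% overstatement is a separate scenario that only better collection of post-tests can address. The actual size in this trial cannot be derived from the protocol, and an SAP may already supply a rule. The change is worth making because it is cheap, and because post-tests that were never collected cannot be recovered at analysis.

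**What to change.** - **IX.1, main analysis.** For continuous outcomes, make the main pre-post analysis a linear mixed model with time (pre, post) as a repeated factor, unstructured covariance and every participant with a baseline value. Keep the paired t-test or Wilcoxon test as a sensitivity analysis in those with both values.
- **IX.1, reporting.** Report baseline values of those with and without a post-test side by side. State that the model corrects only loss explained by observed baseline, not loss of non-responders.
- **VII.2(3).** Make explicit that the post-intervention assessment is offered to all enrolled, whether or not they kept exercising. Settle this before the first participants reach the end of the programme.

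The cost is a few sentences, slightly more analysis work and some effort to recall people who stopped. The estimate may move either way.
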